- 6. Change in additional inflammatory markers from baseline to Week 12:
 - a. IL-10
 - b. TGF-β
- 7. Assessment of change in homeostatic model assessment for insulin resistance (HOMA-IR) from baseline to Week 12

Whole Biome Study No: WB01-202_Ver 2_Amend 3 06/19/18

Page 7 of 45

(https://www.dtu.ox.ac.uk/homacalculator/)

- 8. Assessment of change in the Matsuda index from baseline to Week 12 [Formula for Matsuda index: ISI(comp) = $10,000 / \sqrt{[(G_0 \times I_0)(G_{mean} \times I_{mean})]}$, where
 - G_0 Fasting plasma glucose concentration (mg/dl)
 - I_0 Fasting plasma insulin concentration (mIU/l)
 - G_{mean} Mean plasma glucose concentration during OGTT (mg/dl)
 - OGGT oral glucose tolerance test
 - I_{mean} Mean plasma insulin concentration during OGTT (mU/l)
 - 10,000– Simplifying constant to get numbers from 0 to 12
 - $\sqrt{-}$ Correction of the nonlinear values distribution
- 9. Assessment of change in fasting lipid panel [total cholesterol, LDL cholesterol, HDL cholesterol, and triglycerides (TGs)] from baseline to Weeks 4, 12, and 16
- 10. Change in body weight from baseline to Weeks 2, 4, 12, and 16
- 11. Change in BMI from baseline to Weeks 2, 4, 12, and 16
- 12. Change in waist circumference between baseline and Week 12
- 13. Change in fecal microbiome from baseline to Weeks 4, 12, and 16
- 14. Change in responses to Hospital Anxiety and Depression Scale (HADS) questionnaire from baseline to Week 12
- 15. Change in response to FACIT D&AD and Victoria Bowel Performance Scale Questionnaire

Following completion of the Week 12 visit, subjects will discontinue study product. They will then return to the clinic for a final visit at the end of Week 16, bringing with them a frozen stool sample collected during the prior 3 days to assess the persistence of the administered microorganisms in stool ~4 weeks after discontinuing ingestion. In addition, fasting glucose, insulin, and lipid panel will be collected at Week 16 to evaluate the persistence of changes in these parameters.

E. Study Product Portion Selection:

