A medical history review will be done at screening with interim history reviews at Week 12 and Week 16. A physical examination will be performed at baseline and Week 12. Stool samples will be collected at baseline, Week 4, Week 12, and Week 16. In addition, phone visits will be conducted at Weeks 6 and 10 to collect unsolicited, spontaneous adverse events, review concomitant medications, and access compliance with study product.

The Hospital Anxiety and Depression Scale (HADS) is integrated as part of the EDC system and will be completed at baseline (Visit 1) and week 12 (Visit 7). The FACIT D&AD and Victoria Bowel Performance Scale (BPS) will be optional and completed twice; at week 12 (Visit 7) and again at week 16 (Visit 8). Sites will scan and email or fax the completed optional questionnaires to the sponsor for data entry.

Whole Biome Study No: WB01-202_Ver 2_Amend 3 06/19/18

Page 9 of 45

Figure 1: Overview of Study Design

Screening Visit: -7 to -14 days Consents Inclusion/Exclusion Weight, Vital Signs, BMI, Height History Screening Labs Con Meds + AEs Dispense SCK	Visit 2: Week 2 • Weight, Vital Signs, BMI • Con Meds + AEs • Study Product Compliance • Dispense Study Product • Dispense SCK Visit 3: Week 4	Visit 5: Week 8 Con Meds + AEs Study Product Compliance Dispense Study Product Dispense SCK Visit 6: Week 10 (Phone Visit)	Visit 8: Week 16 Collect SCK Fasting Plasma Glucose Fasting Insulin Fasting Lipid Panel Medical History (Interim) Weight, Vital Signs, BMI Con Meds + Aes
Visit 1: Day 0 Collect SCK Randomization MTT Hemoglobin A1c Fasting Lipid Panel Questionnaires Safety Labs + U/A + Inflammatory Markers Weight, Vital Signs, BMI, Waist Circumference Physical Exam ECG Con Meds + AEs Dispense Study Product	Collect SCK Hemoglobin A1c Fasting Plasma Glucose Fasting Insulin Fasting Lipid Panel Safety Labs + Inflammatory Markers Weight, Vital Signs, BMI Con Meds + AEs Study Product Compliance Dispense Study Product Visit 4: Week 6 (Phone Visit)	Visit 7: Week 12 Collect SCK MTT Hemoglobin A1c Fasting Lipid Panel Questionnaires Safety Labs + U/A + Inflammatory Markers Medical History (Interim) Weight, Vital Signs, BMI, Waist Circumference Physical Exam ECG Con Meds + AEs Dispense SCK	NOTE: Phone Visits (Weeks 6 and 10): Con Meds + AEs Study Product Compliance

Abbreviations: SCK = "Stool Collection Kit"

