- e. Review of concomitant medications
- f. Blood sample collection for the following assessments:
 - i. HIV, Hepatitis C, Hepatitis B, Hepatitis A serologies
 - ii. Serum pregnancy test
 - iii. Chemistry panel (includes glucose, urea nitrogen, creatinine, total protein, albumin, uric acid, total and fractionated bilirubin, alkaline phosphatase, alanine aminotransferase (ALT), aspartate aminotransferase (AST), gamma glutamyltranspeptidase (GGT), creatine phosphokinase (CPK), sodium, potassium, chloride, bicarbonate, phosphate, calcium, and magnesium)
 - iv. Hematology panel (includes red cell count, hemoglobin, hematocrit, white cell count, platelets, differential count, mean cell volume, mean corpuscular hemoglobin, and mean corpuscular hemoglobin concentration)
 - v. Hemoglobin A1c
- g. Review instructions for stool collection [Appendix 2] and dispense a stool collection kit for collection of a stool sample prior to the baseline visit (Visit 1/Day 0). (Note: Subjects should be instructed to freeze the sample in their home freezer immediately after collection and bring the sample frozen to the clinic at their next visit)

2. Baseline (Visit 1/Day 0)

The following procedures will be completed at Visit 1:

a. Physical examination, including vital signs, weight, BMI, and waist circumference

Whole Biome Study No: WB01-202_Ver 2_Amend 3 06/19/18

Page 16 of 45

- b. Review of concomitant medications
- c. Adverse event review
- d. Delivery of the baseline frozen stool sample to clinic staff
- e. Establish venous access for conduct of the standardized Meal Tolerance Test (MTT) according to the procedures outlined in **Appendix 3** (Blood samples for the measurement of plasma glucose and insulin at T=0, 30, 60, 90, 120, and 180 minutes relative to ingestion of a standardized liquid mixed meal (Boost PlusTM, 475 mL = 720 calories)
- f. Using the established venous access, draw bloods for the following **prior to ingestion of the meal:**
 - (i) Chemistry and hematology panels (Safety labs)
 - (ii) Hemoglobin A1c
 - (iii) Fasting total cholesterol, TGs, LDL, and HDL cholesterol (unless included in chemistry panel)
 - (iv) Inflammatory marker panel (CRP, IL-6, IL-10, TNF- α , and TGF- β)
 - (v) 10 mL of blood for a frozen, stored serum sample for the measurement of other hormones, short chain fatty acids, and other metabolites, should study results warrant
- g. ECG
- h. Urine Analysis
- i. Complete Hospital Anxiety and Depression Scale [Appendix 4] questionnaire

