 - (v) 10 mL of blood for a frozen, stored serum sample for the measurement of other hormones, short chain fatty acids, and other metabolites, should study results warrant
- h. Complete Hospital Anxiety and Depression Scale [Appendix 4] questionnaire
- i. Complete **optional** FACIT D&AD Questionnaire and Victoria Bowel Performance Scale (BPS) [**Appendix 5**]
- j. ECG
- k. Urine Analysis
- 1. Review study product compliance
- m. Dispense a stool collection kit for collection of a stool sample within the 3 days prior to the Week 16 visit. (Note: Subjects should be instructed to freeze the sample in their home freezer immediately after collection and bring the sample frozen to the clinic at their next visit)
 - 9. Visit 8 (Week 16)

The following procedures will be completed at Visit 8:

- a. Review interim medical history
- b. Collect vital signs, weight, and BMI
- c. Review of concomitant medications
- d. Non-directed review of adverse events
- e. Complete **optional** FACIT D&AD Questionnaire and Victoria Bowel Performance Scale (BPS) [**Appendix 5**]

Whole Biome Study No: WB01-202_Ver 2_Amend 3 06/19/18

Page 20 of 45

- f. Delivery of a frozen stool sample collected during the prior 3 days to clinic staff
- g. Blood sample collection (**fasting samples**) for the following assessments:
 - (i) Fasting plasma glucose and insulin
 - (ii) Total cholesterol, TGs, LDL, and HDL cholesterol

In addition to the visits to the clinical study site outlined above, all subjects with email and/or text messaging capability will receive an electronic message from their respective clinical study site every second week, starting on Week 4 and ending on Week 10, to remind the subjects which bottle of study product they should be using at that time point and remind them to contact the clinical site with any problems or complaints. The message on Weeks 4, 12, and 16 will be sent 4 days prior to the subjects' upcoming visit to remind the subjects to collect their stool samples and bring them to their next clinic visit.

O. Ethical Safety Considerations:

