=	0	Definitely	0	Š.	Often
	1	Usually	1		Sometimes
	2	Not Often	2		Not often
_	3	Not at all	3		Very seldom

Please check you have answered all the questions

Scorin	ng:		
Total	score: Depression (D)	Anxiety (A)	
0-7	= Normal		
8-10	= Borderline abnormal (border	line case)	
11-21	= Abnormal (case)		

Whole Biome Study No: WB01-202_Ver 2_Amend 3 06/19/18

Page 40 of 45

Appendix 5

WB01-202 Subject Optional Questionnaire FACIT-D & AD (V.4) & Victoria Bowel Performance Scale (BPS)

Please look at the Victoria Bowel Performance Scale below and circle the BPS (e.g. -2) that most closely resembles your bowel movements.

				Victoria B	owel Perforr	nance Scale			
Constipation					Normal			Diarrhea	
Visit 7/Week 12 (last day of treatment)	-4	-3	-2	-1	G	+1	+2	+3	+4
Visit 8/Week 16 (4 weeks after treatment)	-4	-3	-2	-1	G	+1	+2	+3	+4

CTORIA DSPICE										
- 4	- 3	- 2	-1	BPS Score G	+1	+ 2	+ 3	+4		
		Constipation		Normal		Diarrhea	_			
Impacted or Obstructed +/- small leakage	Formed Hard with pellets	Formed Hard	Formed Solid	Characteristics Formed Semi-solid	Formed Soft	Unformed Loose or paste-like	Unformed Liquid ±mucous	Unformed Liquid ±mucous		
No stool produced after Goal plus 3 days	Goal plus 3 or more days delay	Goal plus 1-2 days delay	Patient's Goal frequency occurs	Pattern Patient's Goal for frequency	Patient's Goal frequency occurs	Goal or more frequent than goal	More frequent than goal	More frequent than goal		
Unable to defecate despite maximum effort or straining	Major effort or straining required to defecate	Moderate effort or straining required to defecate	Minimal or no effort required to defecate	Control Minimal or no effort to defecate	Minimal or no effort required to control urgency	Moderate effort required to control urgency	Very difficult to control urgency and may be explosive	Incontinent or explosive; unable to control or unaware		

Instructions for Use

- BPS is a 9-point scale. It is a single score, based on the overall 'best vertical fit' among the above three parameters [characteristics, pattern, control] and is recorded for example as: BPS +1, BPS -3 or
- Look vertically down each BPS level to become familiar with how the three parameters of characteristics, pattern & control change in gradation from constipation to diarrhea
- Look vertically down each BYS level to become annihilar with now the three parameters of characteristics, pattern a control change in gradation from constipation to diarrhea.

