Please circle or mark one number per line to indicate your response as it applies to the past 7 days.

	ADDITIONAL CONCERNS	Not at all	A little bit	Some- what	Quite a bit	Very much
О3	I have cramps in my stomach area	0	1	2	3	4
ACT11	I have pain in my stomach area	0	1	2	3	4
AD1	Stomach pain interferes with my daily functioning	0	1	2	3	4

Have you noticed any other changes since starting the study?					

~ Thank You ~

Subject Initials	Subject No	Visit 7 / Visit 8 (circle one)	Date//	

Whole Biome Study No: WB01-202_Ver 2_Amend 3 06/19/18

Page 45 of 45

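### Secondary endpoint 15 is a change in FACIT D&AD and bowel scale scores with no time points, and neither form is collected before Week 12, so change from baseline cannot be computed

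*Protocol*

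**What the plan says.** Protocol sections D and S both list endpoint 15 as "Change in response to FACIT D&AD and Victoria Bowel Performance Scale Questionnaire", with no time points. Endpoint 14, directly above it, is fully specified: "Change in responses to Hospital Anxiety and Depression Scale (HADS) questionnaire from baseline to Week 12". Endpoints 1 to 13 also name baseline as their reference.

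Section F sets the schedule for FACIT D&AD and BPS: they "will be optional and completed twice; at week 12 (Visit 7) and again at week 16 (Visit 8"). The visit lists in section N agree. The only questionnaire at Visit 1 is HADS ("Complete Hospital Anxiety and Depression Scale [Appendix 4] questionnaire"), while the optional "FACIT D&AD Questionnaire and Victoria Bowel Performance Scale (BPS") appears at Visits 7 and 8. The BPS form in Appendix 5 has two rows, "Visit 7/Week 12 (last day of treatment") and "Visit 8/Week 16 (4 weeks after treatment"), and none for Day 0.

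Section F also says that product stops at the Week 12 visit and a 4-week washout follows.

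**The concern.** A change endpoint needs a reference value. Here the first value is taken after 12 weeks on product, so nobody's bowel or quality-of-life score before product is known. The one change that can be computed compares the last day on product with four weeks off it. That is a withdrawal contrast, and the protocol does not say that it is the one intended.

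The forms matter more than the endpoint's place in the list suggests. Safety and tolerability is a primary objective, two of the strains are new to humans (section C), and adverse event review at the treatment visits is non-directed. These are the only structured gastrointestinal symptom instruments the protocol describes. A statistical analysis plan can name the contrast, but it cannot supply a Day 0 measurement that was never taken.

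**Working it through.** The protocol states no figure for this endpoint and no alpha, power, effect size or standard deviation (section U), so there is nothing to reproduce. The check has two parts.

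**1. Assessments available per subject**

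| Time | Product status | HADS | FACIT D&AD and BPS |
|---|---|---|---|
| Day 0 (Visit 1) | before product | yes | no |
| Week 12 (Visit 7) | last day on product | yes | optional |
| Week 16 (Visit 8) | 4 weeks off product | no | optional |

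Appendix 1 marks an unnamed questionnaires row at Day 0, Week 12 and Week 16. The Day 0 mark is accounted for by HADS, so it does not imply a baseline FACIT or BPS. The count for FACIT and BPS is 0 before product, 1 on product and 1 off product.

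Three contrasts follow:

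- Day 0 to Week 12 within subject: not computable.
- Week 12 to Week 16 within subject: computable, and comparable between arms, but it describes stopping product. Week 16 cannot stand in for baseline, because the protocol itself tests whether the organisms persist in stool at that visit. If effects persist too, this change could be near zero despite a real effect on product.
- Week 12 score between arms: computable, and it estimates the on-product effect through randomization.

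**2. What the missing baseline costs the Week 12 comparison (illustration)**

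From the protocol: about 60 completers, about 20 per arm (section H). Assumed: two-sided alpha 0.05, 80% power, normal approximation, and correlation r between baseline and Week 12 scores of 0.3 to 0.7.

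Residual variance after baseline adjustment, relative to none, is 1 − r²:

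- r = 0.3: 1 − 0.09 = 0.91, a 9% cut
- r = 0.5: 1 − 0.25 = 0.75, a 25% cut
- r = 0.7: 1 − 0.49 = 0.51, a 49% cut

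The detectable difference between two arms, in SD units, without baseline is (1.960 + 0.842) × √(2/n):

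- n = 20: 2.802 × 0.316 = 0.89
- n = 15 responders: 1.02
- n = 10 responders: 1.25

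With a Day 0 score and n = 20, multiply 0.89 by √(1 − r²) for baseline-adjusted analysis (ANCOVA), or by √(2(1 − r)) for a simple change score:

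| r | ANCOVA | Simple change |
|---|---|---|
| 0.3 | 0.85 | 1.05 |
| 0.5 | 0.77 | 0.89 |
| 0.7 | 0.63 | 0.69 |

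At r = 0.3 a simple change score does worse than Week 12 scores alone (1.05 against 0.89), and at r = 0.5 it only breaks even. The gain comes from adjusting for baseline, not merely from subtracting it.

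**The case against.** Endpoint 15 says change, not change from baseline. The form's two rows are the last day of treatment and four weeks later, and section D shows an interest in what happens after product is stopped. On that reading the design is a coherent on/off comparison and only lacks stated time points. This stands in part: the text does not flatly contradict itself. But nothing says that a withdrawal contrast was intended, and every other secondary endpoint is referred to baseline.

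A reader might go further and infer that no effect of taking the product can be measured, or that existing bowel symptoms cannot be told apart from product effects. The protocol does not support that. The trial is randomized, double-blind and placebo-controlled. Prior symptoms are balanced in expectation, active GI disease is excluded, and the Week 12 comparison between arms estimates the on-product effect. BPS is also scored against the subject's own goal frequency, so a single score carries some self-reference. What is lost is precision and any check on chance imbalance. Optional completion adds a separate weakness, since responders are selected after randomization.

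A reader might also infer that symptoms written on these forms, including under "Have you noticed any other changes since starting the study", bypass the adverse event record because the sponsor enters the data. Section F has the sites scan and send the forms, and both visits include an adverse event review. No step requires staff to screen the forms, but a bypass is not shown.

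Finally, the primary safety endpoint is the incidence of treatment-emergent adverse events, and no primary conclusion depends on endpoint 15. That stands and limits the severity.

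**Conclusion.** The concern holds in limited form. The schedule, which is consistent across section F, section N and Appendix 5, leaves endpoint 15 with no baseline. Its only computable change spans the stopping of product, and its time points are not stated. An on-product effect can be assessed only by comparing arms at Week 12, unadjusted for baseline, among volunteers in arms of about 20.

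The loss of efficiency depends on a correlation the protocol does not give: 9% of residual variance at r = 0.3, 25% at 0.5 and 49% at 0.7. At 20 per arm, and under the assumed alpha and power, a detectable difference of 0.89 SD would fall to between 0.85 and 0.63 SD with adjustment.

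Severity is minor to moderate. This is the last of 15 secondary endpoints in an exploratory trial, but the remedy is cheap and a missed baseline cannot be recovered later.

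**What to change.** - Add FACIT D&AD and BPS to the Visit 1 list in section N, before the first capsules are taken. Change the schedule sentence in section F to match, and add a Day 0 row and visit label to the Appendix 5 form. Appendix 1 already marks questionnaires at Day 0.
- In sections D and S, define endpoint 15 as the between-arm comparison of change from Day 0 to Week 12, adjusted for the Day 0 score.
- Report Week 12 to Week 16 separately, as a description of the washout.
- For subjects already past Day 0, restate the endpoint as a between-arm comparison of Week 12 scores. The adjusted analysis targets the same Week 12 difference between arms, so the two remain compatible.

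The cost is a short protocol and form amendment with IRB approval, and a few more minutes at a visit where HADS is already completed. Making the forms mandatory, or having site staff read them for adverse events, could be considered in the same amendment, but the point does not depend on either.
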